2.2 Randomization

Randomization will occur cluster-wise on level of the practices where the enrolled GPs work. A statistician external to the study group will carry out stratified randomization into the active or control intervention group using the Shiny Balancer tool, which facilitates balanced allocation in cluster-randomised trials (1).

Stratification will occur according to the following factors:

- Participation status in the cantonal HPVv program at inclusion (yes/no).
- Estimated number of HPVv administered during the baseline period (4 categories, see section 3.3.1).

GPs enrolling in the trial when randomization of their practice has already taken place will be allocated to the corresponding study arm. GPs will need to be registered in the cantonal HPVv program before initiation of outcome measurements.

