3.3.2 Outcome Measurements

GPs will document all vaccines administered to patients aged at least 18 years starting on T0 and ending on T12. We will provide enrolled GPs with separate standardized case report forms (CRFs) to report all vaccinations administered during the study period and the follow-up period, respectively. GPs will report the following vaccinations: HPV, MMR, meningococci, pneumococci, TBE, chickenpox, shingles, and hepatitis A/B (combination and individual vaccines). The GPs will send CRFs to the Institute of Primary Care every two months by mail. For the study period and the follow-up period, GPs will report age and sex of patients to whom these vaccines are administered. In addition, only during the study period, they will report whether vaccinations are administered as first/second/third doses or as booster vaccinations as well as whether they are administered upon request by the patient or as recommended by the GP. During the follow-up period, they will only indicate whether vaccinations are administered as first or later doses (without further specification).

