4.1.2 Secondary Objectives

- (1) To compare the first-dose HPVv counts at T3 and T12 between the intervention group and the control group.
- (2) To compare the number of overall HPVv counts at T3, T6, and T12 between the intervention group and the control group.
- (3) To compare the change of overall HPVv counts at T3, T6 and T12 with respect to Pb between the intervention group and the control group.
- (4) To compare the change in HPV-related knowledge at T6 with respect to Ti (before delivery of the intervention) between the active intervention group and the control group.
- (5) To compare the change in attitudes towards HPVv at T6 with respect to Ti (before delivery of the intervention) between the active intervention group and the control group.
- (6) To describe demographic characteristics of patients obtaining HPVv (gender and age).
- (7) To describe the following characteristics of administered HPVv: first dose or later vaccination, request of patient or recommendation by GP (or both), and HPVv administered alone or in combination with other vaccines.

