4.2 Analysis Methods

4.2.1 Descriptive and Baseline Analyses

For all descriptive analyses, we will report counts and percentages for categorical variables and extreme values (minimum and maximum), means and standard deviations, and medians and upper/lower quartiles for continuous variables.

We will provide descriptive summaries for demographic characteristics of participating GPs (age, gender, years of experience in practice, type of practice, type of employment, and workload) and for characteristics of patients who will be administered HPVv (age and gender).

To assess differences in baseline characteristics of GPs in the ITT population among the study arms, we will use Pearson's chi-squared and Fisher's exact tests for categorical variables and Student's *t*-tests and Wilcoxon rank-sum tests for continuous variables as appropriate. The same tests will be performed to assess differences between GPs of the ITT population and GPs lost to follow-up.

We will assess differences of HPVv counts during the study period between the study arms using Pearson's chi-squared and Fisher's exact tests. Cochran Armitage trend test will be used for comparison of HPVv counts between the study arms using the measurement time point as an ordinal variable (with levels T3, T6, T12).

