4.2.3 Analysis of the Primary Objective

To analyze the primary objective, we will model the count of first administered HPVv doses at T6 using mixed-effect Poisson regression. The outcome variable will be the count of first HPVv doses administered by each GP at each of the time points T3 or T6. GP-level random intercepts will account for intra-GP correlation. The following fixed effects will define the grouping variables of the data set:

- Study arm (binary with levels control; active)
- Time point (binary with levels T3; T6)
- Baseline HPVv count (categorical with levels Never; Rarely (1–5 doses); Occasionally (6–10 doses); Regularly (at least 11 doses))
- GP gender (binary with levels male; female)
- GP age in years (continuous)
- GP workload (categorical with levels < 60%; 60–79%; 80–100%; based on the distribution of consultation counts according to workload in Swiss primary care (4))
- GP participation status in the cantonal HPVv program at inclusion (binary with levels yes; no)
- Patient gender (binary with levels male; female).

Each fixed effect other than the study arm will be included in the final model if a corresponding univariate analysis results in a *p*-value ≤ 0.2 .

The Poisson regression model will be assessed for overdispersion based on an asymptotic chi-squared test for the sum of squared residuals (5, 6). If the null hypothesis of no overdispersion is rejected at the 0.05 level, we will replace the Poisson model by a negative binomial model with the same fixed- and random-effect structure. A quasi-Poisson model will be considered as an alternative in case of an observed linear variance-to-mean relationship (7).

Rejection of the null hypothesis related to the primary objective (the effect associated with the study arm is equal to zero) will be based on the parameter estimate of study arm and its 95% confidence interval in the final model.

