4.2.4 Analysis of the Secondary Objectives

For the secondary objectives, we will use the following procedures:

- (1) Analogous models as for the primary objective, using the first HPVv dose count at the respective time point and assessing the coefficient estimate of the study arm together with 95% confidence intervals.
- (2) Analogous models as for the primary objective, but using the count of all administered HPVv doses instead of the number of first HPVv doses at the respective time points as the outcome variable. We will base assessment of this objective on the estimated coefficient of the study arm for the respective time points together with 95% confidence intervals.
- (3) We will model this objective with logistic regression. The binary outcome variable will indicate whether the overall count of administered HPVv doses at T6 will have increased with respect to the value indicated for Pb. Model covariates will include GP gender, workload (categorized as for the primary objective), and participation status in the cantonal HPVv program at inclusion.
- (4) To assess this objective, we will use logistic regression on a binary outcome indicating, for each GP, whether their HPV knowledge score will have increased from Ti to T6. The model will include the following covariates: study arm, baseline HPV knowledge score, GP gender, GP workload (categorized as for the primary objective), and participation status in the cantonal HPVv program at inclusion.
- (5) We will assess this objective by a logistic regression model analogous to the model for secondary objective 4. The binary outcome variable will indicate, for each GP, whether their HPVv attitude score will have increased from Ti to T6. Adjustment will occur for the baseline HPVv attitude score instead of the HPV knowledge score.
- (6) Tabulation and assessment of group differences as described in section 4.2.1.
- (7) Tabulation and assessment of group differences as described in section 4.2.1.

For each of the fitted regression models, we will report the results and inferred implications of standard model diagnostics procedures, such as assessment for overdispersion, residual and random effect analyses, influential point analyses, and checks for multicollinearity. Accordingly, we will adapt models as necessary (e.g., by log-transforming continuous variables, by excluding ill-defined variables from the model equations or by considering non-parametric alternatives where deemed appropriate).

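### Objective 7 compares characteristics of HPV doses between arms with chi-squared or Fisher's exact tests that ignore clustering by GP and practice

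*SAP*

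**What the plan says.** SAP 4.1.2 item (7) sets the objective: "To describe the following characteristics of administered HPVv: first dose or later vaccination, request of patient or recommendation by GP (or both", followed by whether the dose was given alone or with other vaccines. For its analysis, SAP 4.2.4 item (7) prescribes "Tabulation and assessment of group differences as described in section 4.2.1".

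In SAP 4.2.1, "we will report counts and percentages for categorical variables" covers the tabulation. On testing, "we will use Pearson's chi-squared and Fisher's exact tests for categorical variables" is written there for GP baseline characteristics, and "We will assess differences of HPVv counts during the study period between the study arms using Pearson's chi-squared and Fisher's exact tests" covers dose counts. Neither sentence mentions clustering or a summary per GP.

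SAP 3.3.2 has GPs report for each vaccination, in the study period only, "whether they are administered upon request by the patient or as recommended by the GP". In the follow-up period only first versus later dose is recorded.

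On the design, SAP 2.2 states: "Randomization will occur cluster-wise on level of the practices where the enrolled GPs work". For the primary model, SAP 4.2.3 states: "GP-level random intercepts will account for intra-GP correlation". A practice-level intercept appears only in a sensitivity analysis of the primary objective (SAP 4.2.5). SAP 3.1 sets the 0.05 level for all analyses and makes the secondary outcomes exploratory, without multiplicity adjustment.

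**The concern.** The objective is descriptive, but its analysis is a between-arm test. Followed as written, that test is a contingency table of doses by arm. Doses from one GP share that GP's way of raising HPV vaccination, and arms are assigned by practice. The SAP accepts the first fact for its primary outcome but does not carry it over to objective 7. If doses within a GP are positively correlated, the test overstates the information in the data, and a difference between a few GPs can appear as a significant difference between arms. What is at stake is a false signal about how doses came to be given. Readers are likely to look at that table, because the training concerns how GPs recommend the vaccine.

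**Working it through.** **Unit of analysis.** The SAP does not state it. The objective speaks of characteristics of administered doses, the form records them per vaccination, and no share per GP or per practice is defined. A pooled table of doses is therefore an inference, but it is the only unit for which the SAP supplies data and a test without a further definition.

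**Plan's own figure.** There is none for objective 7. The sample size statement in SAP 2.4 concerns another quantity and gives no ICC.

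**Inputs.** From the SAP: two-sided alpha 0.05, randomisation by practice, recording per dose. Assumed: m = 5 or 10 doses per GP and ICC = 0.05 to 0.3. For orientation on m, the baseline categories in SAP 3.3.1 are 1–5, 6–10 and at least 11 doses in three months. Doubled to the six-month study period, the first two become 2–10 and 12–20.

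**Formula.** Design effect DE = 1 + (m − 1) × ICC. True size of an unadjusted two-sided 5% test = 2 × [1 − Φ(1.96/√DE)]. Example: m = 10, ICC = 0.1 gives DE = 1 + 9 × 0.1 = 1.9 and a size of 15.5%.

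| Doses per GP (equal) | ICC 0.05 | ICC 0.1 | ICC 0.2 | ICC 0.3 |
|---|---|---|---|---|
| 5: DE | 1.20 | 1.40 | 1.80 | 2.20 |
| 5: true size | 7.4% | 9.8% | 14.4% | 18.6% |
| 10: DE | 1.45 | 1.90 | 2.80 | 3.70 |
| 10: true size | 10.4% | 15.5% | 24.1% | 30.8% |

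The standard error is too small by a factor √DE: 1.10 at the mildest setting (√1.20) and 1.92 at the strongest (√3.70).

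**Simulation check.** Beta-binomial data, true share 50% in both arms, 5,000 runs per setting, mean 5 or 10 doses per GP, and 16 or 33 GPs per arm, because SAP 2.4 does not say whether its 33 GPs are the total or per arm.
- Pooled chi-squared, Poisson dose numbers: 7.4% to 33.1% false positives.
- Pooled chi-squared, very uneven dose numbers (negative binomial, dispersion 1): 10.1% to 46.2%.
- One share per GP, t-test across GPs: 4.5% to 5.8%.

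Results for 16 and 33 GPs per arm are nearly the same, so the ambiguity in SAP 2.4 does not matter here. The simulation contains no practice effect. Fisher's exact test rests on the same independence assumption.

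**What the share can and cannot show (hypothetical counts).** Control 64 recommended + 64 requested against active 128 + 128: recommended doses double, the share is 50% in both arms, chi-squared p = 1.0. Control 64 + 64 against active 64 + 16: recommended doses are unchanged, the share goes from 50% to 80%, p = 0.000015. The share has doses given as its denominator, and the intervention is meant to raise that denominator.

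**The case against.** The objective says only that characteristics will be described. SAP 3.1 makes secondary outcomes exploratory and promises caution with their p-values. The unit of analysis is not written down, and the size of the error rests entirely on assumed values. All of this is true and limits the weight of the point. It does not remove it: exploratory status excuses the lack of multiplicity adjustment, but not a p-value computed as if doses were independent, and caution is no guide to how far that p-value is off.

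Three stronger readings are tempting, and the SAP does not support them.
- A reader might infer that objective 7 fails as a measure of whether the training raised GP-recommended first doses. The SAP never claims that it measures this. Counts are tabulated beside percentages, so both hypothetical patterns above would be visible, and first-dose and overall counts have their own models with GP intercepts. What remains is that no model targets GP-recommended first doses.
- A reader might infer that this is the only process evidence in the trial. Changes in knowledge and attitude are compared between arms under objectives 4 and 5, although they do not record behaviour at the vaccination itself.
- A reader might infer that the standard error is always far too small. At 5 doses per GP and an ICC of 0.05 it is off by a factor of 1.10, and the true size is about 7%.

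**Conclusion.** The point holds for the test, not for the table. Under its natural reading, SAP 4.2.4 item (7) with 4.2.1 yields p-values that are too small whenever the within-GP correlation is positive. With equal dose numbers of 5 to 10 per GP and an ICC of 0.05 to 0.3, a nominal 5% test has a true size of about 7% to 31%. Uneven dose numbers raise this further. The direction needs only a positive correlation; the magnitude depends on an ICC and dose numbers that the SAP does not give. The objective is secondary and exploratory, and the primary conclusion does not depend on it.

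**What to change.** In SAP 4.2.4 item (7), do one of the following:
- Present the characteristics by arm as counts and percentages, without p-values. This matches the wording of the objective.
- Keep a comparison, but state the unit and respect clustering: for example one share per GP compared across GPs, or a logistic model with GP and practice random intercepts. Where a practice supplies several GPs, one share per practice is the safer summary. GPs with no HPV dose have no share and drop out, which should be reported.

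Optional exploratory addition: cross origin with first dose and form two T0–T6 counts per GP, namely first doses recommended by the GP (including those marked as both) and first doses requested by the patient only. Model each with study arm, a practice random intercept and an allowance for overdispersion, and report rate ratios with 95% confidence intervals. The terms need spelling out: with a single count per GP, a GP intercept acts as an overdispersion term and not as a clustering term. Origin is reported by the GP, and active-arm GPs may label the same encounter differently after training, so these ratios would not be clean evidence that the taught style was used.

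Cost: a sentence in the SAP, and one or two model fits if a comparison is kept. No new data are needed. Intervals that respect clustering will be wider than the pooled test suggests.

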4.2 Analysis Methods

4.2.1 Descriptive and Baseline Analyses

For all descriptive analyses, we will report counts and percentages for categorical variables and extreme values (minimum and maximum), means and standard deviations, and medians and upper/lower quartiles for continuous variables.

We will provide descriptive summaries for demographic characteristics of participating GPs (age, gender, years of experience in practice, type of practice, type of employment, and workload) and for characteristics of patients who will be administered HPVv (age and gender).

To assess differences in baseline characteristics of GPs in the ITT population among the study arms, we will use Pearson's chi-squared and Fisher's exact tests for categorical variables and Student's *t*-tests and Wilcoxon rank-sum tests for continuous variables as appropriate. The same tests will be performed to assess differences between GPs of the ITT population and GPs lost to follow-up.

We will assess differences of HPVv counts during the study period between the study arms using Pearson's chi-squared and Fisher's exact tests. Cochran Armitage trend test will be used for comparison of HPVv counts between the study arms using the measurement time point as an ordinal variable (with levels T3, T6, T12).

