3.1 Confidence Intervals and *p*-Values

We will report statistical significance as determined in statistical null hypothesis tests by means of p-values. A level of significance of 0.05 will be used throughout the analyses. Accordingly, we will report two-sided 95% confidence intervals of coefficient estimates.

We will use a mixed-effects regression model for assessment of the primary objective and we will base rejection of the null hypothesis (no difference in effect on HPVv counts at T6 between the control and

intervention group related to the study hypothesis (see section 1.2) on statistical significance of a specific fixed effect coefficient estimate (see section 4.2.3).

Secondary outcomes will be assessed in an exploratory manner, and no adjustment for multiplicity will be implemented. We will judge resulting *p*-values with appropriate caution and consider the corresponding effect sizes.

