3.2 Analysis Populations

For each of the primary and secondary objectives, we will define an intention-to-treat analysis (ITT) population as the population of all GPs who underwent randomization, regardless of participation in the educational session at Ti and loss to follow-up.

For each of the primary and secondary objectives, a per-protocol analysis (PPA) population will include all GPs who participated in the educational session at Ti.

Handling of missing data in the ITT and PPA populations is described in section 4.3.

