4.3 Missing Data

Missing data may potentially occur on two levels:

- GPs: baseline (including demographic) characteristics, failure to undergo the intervention, failure to return CRFs (including loss to follow-up) or questionnaires.
- Patients (data from the CRFs): demographic characteristics, type of vaccination.

To analyze the study objectives, we will use the following procedures to handle missingness in the ITT and PPA population data sets:

- Loss to follow-up of GPs: complete-case analysis.
- Missing baseline characteristics of GPs and missing patient-level characteristics: complete-case analysis.

For each study objective, we will conduct a sensitivity analysis on the IIT population using multilevel chained equations-based multiple imputation with 5 datasets and 20 iterations. We will restrict use of multiple imputation to this sensitivity analysis and use a complete-case approach for the main analysis due to the low anticipated drop-out rates (2).

For other analyses not belonging to a study objective, we will handle missing data by pairwise deletion (i.e., by omitting only cases with missing values of variables relevant to the current analysis).

The nature and frequency of missing data will be reported for all analyses. Differences in loss to followup frequencies between the study arms will be assessed using Pearson's chi-squared and Fisher's exact test.

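### The attrition check in SAP 4.2.1 compares GPs lost to follow-up with an ITT population that contains them, so its tests are conservative and understate how lost GPs differ

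*SAP*

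**What the plan says.** Section 4.2.1 first sets out how baseline characteristics are compared between arms: "we will use Pearson's chi-squared and Fisher's exact tests for categorical variables", and Student's t or Wilcoxon rank-sum tests for continuous ones. It then extends these tests to attrition, where they serve "to assess differences between GPs of the ITT population and GPs lost to follow-up".

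Section 3.2 defines the ITT population as the "population of all GPs who underwent randomization, regardless of participation in the educational session at Ti and loss to follow-up".

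Section 4.3 handles lost GPs in the analyses of the study objectives as follows: "Loss to follow-up of GPs: complete-case analysis". It adds a multiple-imputation sensitivity analysis for each objective, a between-arm test of how often GPs were lost, and reporting of the nature and frequency of missing data.

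Section 3.1 fixes the threshold: "A level of significance of 0.05 will be used throughout the analyses".

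**The concern.** By the definition in section 3.2, every GP lost to follow-up is also an ITT GP. The four tests named in section 4.2.1 assume two separate groups. Applied as written, they enter each lost GP twice, once on each side. This has two effects, both in the same direction. The ITT mean or proportion is pulled towards that of the lost GPs, and the standard error formula ignores the positive correlation between the two groups and so comes out too large.

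What is at stake is how attrition is interpreted. The main analysis drops lost GPs, so readers will want to know whether those GPs resembled the ones who stayed. No other planned comparison looks at the characteristics of lost GPs; the between-arm test in section 4.3 concerns only how many were lost. A check that leans towards finding no difference may reassure more than the data warrant.

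**Working it through.** The SAP states no figure for this comparison, so there is nothing of its own to reproduce.

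**Inputs**
- Groups compared: ITT population and lost GPs (section 4.2.1); ITT includes the lost (section 3.2).
- Nominal level: 0.05, two-sided (section 3.1).
- Number of GPs: section 2.4 gives 33 without saying whether this is the total or per arm, so both 33 and 66 are used as totals.
- Share lost, d: not given. Section 4.3 says only that low drop-out is anticipated. A range of 5% to 30% is assumed, with 5% to 15% taken as the most relevant part.

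**Algebra.** Let N be the number of ITT GPs, m the number lost, d = m/N, and s a common SD.
1. The ITT mean is d × mean(lost) + (1 − d) × mean(retained). Hence mean(lost) − mean(ITT) = (1 − d) × [mean(lost) − mean(retained)].
2. The independent-samples test assumes the variance s²(1/m + 1/N). The true variance, given the overlap, is s²(1/m − 1/N).
3. The z statistic for lost versus retained has denominator s√(1/m + 1/(N − m)). Dividing the overlapping z by this disjoint z gives r = √((1 − d)/(1 + d)).
4. The overlapping test therefore rejects only when the correct |z| exceeds 1.96/r. Actual type I error = 2 × [1 − Φ(1.96/r)]. If the correct test has 80% power, its mean z is 1.960 + 0.842 = 2.802, and the overlapping test has power 1 − Φ(1.96/r − 2.802).

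For d = 10%: r = √(0.90/1.10) = 0.9045; 1.96/0.9045 = 2.167; type I error = 0.030; power = 1 − Φ(−0.635) = 0.737.

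| Assumed loss d | Factor on difference | Factor on z | Actual type I error | Power (correct test 80%) |
|---|---|---|---|---|
| 5% | 0.95 | 0.951 | 0.039 | 77% |
| 10% | 0.90 | 0.905 | 0.030 | 74% |
| 15% | 0.85 | 0.860 | 0.023 | 70% |
| 20% | 0.80 | 0.816 | 0.016 | 66% |
| 30% | 0.70 | 0.734 | 0.008 | 55% |

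These are large-sample figures. They depend only on d, so the ambiguity over 33 or 66 does not affect them.

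**Small-sample check.** Student's t-tests were simulated (20,000 runs per setting), with an assumed 1-SD shift for power:

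| N, lost | Type I error: as written / lost vs retained | Power: as written / lost vs retained |
|---|---|---|
| 33, 3 | 0.025 / 0.048 | 0.25 / 0.36 |
| 66, 7 | 0.026 / 0.050 | 0.59 / 0.69 |
| 33, 7 | 0.011 / 0.051 | 0.38 / 0.62 |
| 66, 13 | 0.014 / 0.050 | 0.76 / 0.89 |

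**Categorical illustration** (invented counts). With 7 of 66 lost, and a characteristic present in 5/7 lost and 20/59 retained GPs, Fisher's p is 0.095 against the retained and 0.116 against the ITT population (25/66). With 13 lost, and 9/13 against 18/53, p is 0.029 against the retained and 0.074 against the ITT population (27/66). The second case crosses 0.05, but it assumes 20% loss.

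**The case against.** The authors may simply have meant lost versus retained GPs. Section 4.3 applies complete-case handling to the ITT data sets, so the ITT data as analysed for the objectives exclude lost GPs and do not overlap with them. That makes loose wording a fair guess. It does not cure the sentence: the complete-case rule is stated for the study objectives, and no section changes who belongs to the ITT population or redefines the comparator here.

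It can also be said that little depends on the result. This largely stands. The complete-case analysis and the imputation analysis are fixed whatever the check shows, and the primary test does not use it. A reader might infer that this comparison is the plan's sole protection against selective loss; section 4.3 does not support that, given its multiple-imputation analysis, its between-arm test of loss frequency (which has no overlap) and its reporting of missingness. A reader might also infer false positives from the term invalid test; the error runs the other way, since the test rejects too rarely.

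Finally, few lost GPs limit any version of the test. With 3 of 33 lost, the correct comparison detects a 1-SD difference only 36% of the time, so a non-significant result would be weak reassurance even after correction. That also stands, but it is no reason to keep the overlap.

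**Conclusion.** The point holds as a minor error of specification. Read with section 3.2, section 4.2.1 tests a group against its own subset with methods that require separate groups, and the p-values come out too large.

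If drop-out is as low as the SAP expects, the effect is modest: z falls by about 5% at 5% loss and 10% at 10% loss. It grows with the share lost. The direction follows from the algebra; the size rests on assumed loss rates, a common SD and, for the simulated power, an assumed 1-SD shift. Larger distortions can be produced with losses of 20% or more, but nothing in the SAP suggests losses of that order are expected.

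The defect is confined to the baseline comparison of lost GPs. It gives no ground for doubting the primary analysis or the between-arm comparison of loss frequency.

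**What to change.** In the attrition sentence of section 4.2.1, restrict the comparator to ITT GPs who completed follow-up, so that lost GPs are compared with retained GPs. The same tests can then stand; in the simulations shown, this restores the type I error to 0.048–0.051.

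Standardised differences beside the p-values would be useful with so few lost GPs, but are optional. Separate testing by arm is not needed, as the lost GPs in each arm would be too few to support it.

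The cost is one phrase in the SAP. No new data, no change to the sample size and no change to any other analysis are required.

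### Section 4.2.1 tests HPVv counts by arm with a trend test that cannot see a constant arm effect, and with chi-squared and Fisher tests whose unit and table are undefined

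*SAP*

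**What the plan says.** SAP section 4.2.1, under descriptive and baseline analyses, contains two inferential sentences on HPVv counts. The one on arm differences within a single window reads: "We will assess differences of HPVv counts during the study period between the study arms using Pearson's chi-squared and Fisher's exact tests".

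The other concerns the course over the follow-up visits, with T3, T6 and T12 as the levels, and reads: "Cochran Armitage trend test will be used for comparison of HPVv counts between the study arms using the measurement time point as an ordinal variable".

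Neither sentence gives the unit of analysis, the table layout, a denominator or an allowance for clustering. Neither says whether first doses or all doses are meant.

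Elsewhere the SAP recognises the structure of these data:

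- Section 2.2: "Randomization will occur cluster-wise on level of the practices where the enrolled GPs work".
- Section 4.2.3 on the outcome: "The outcome variable will be the count of first HPVv doses administered by each GP at each of the time points T3 or T6".
- The same section on correlation within a GP: "GP-level random intercepts will account for intra-GP correlation". If overdispersion is found, "we will replace the Poisson model by a negative binomial model with the same fixed- and random-effect structure".
- Section 4.2.5 adds practice-level intercepts as a sensitivity analysis.
- Section 7 defines the outcomes as uptake from T0 up to each time point.

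For secondary objectives 6 and 7, section 4.2.4 specifies "Tabulation and assessment of group differences as described in section 4.2.1". Section 3.1 applies the 0.05 level to all analyses.

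**The concern.** There are two separate defects.

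**Cochran-Armitage.** The test needs one binary and one ordinal variable. With time point as the ordinal variable, the only binary variable left is the arm in which each dose was given. The test then concerns a change in the arms' shares over time, not a difference in counts between arms. A reader of the final report could take a non-significant result as evidence against an arm effect that the test was not able to detect.

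**Pearson and Fisher.** These tests need independent units sorted into categories. The outcome is a count per GP, and under section 3.3.2 GPs document only vaccines administered, so no unvaccinated group makes a dose a yes/no outcome. An analyst has to invent the table. One natural choice, pooling doses by arm, ignores the within-GP correlation that section 4.2.3 models. Another, GPs grouped by count, does not.

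At stake are p-values at the 0.05 level on HPVv counts by arm that may disagree with the mixed model, and group tests for objectives 6 and 7 that treat clustered patients and doses as independent.

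**Working it through.** The SAP attaches no figure to these tests, so there is none to reproduce. Doses per GP and between-GP variance are not in the SAP; they are assumed and shown as ranges.

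**1. What the trend test measures.** Let the control arm give n_t doses at level t and the active arm ρ·n_t. The active share is ρ/(1+ρ) at every level, cumulative or not: 1.57/2.57 = 0.611 for ρ = 1.57, and 2/3 = 0.667 for ρ = 2. The statistic is T = Σ s_t(a_t − N_t·p), where a_t is the active count, N_t the total, s_t the score and p the overall active share. If every level has share p, the expected value of T is zero whatever the size of ρ.

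**2. Overlap.** If counts run from T0, a dose given in T0–T3 enters three columns, one in T3–T6 two, and one in T6–T12 one. At a steady rate the columns are in proportion 3 : 6 : 12 months, so 12 months of doses produce 21 entries, or 21/12 = 1.75 per dose.

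**3. Simulated trend test.** GP counts were gamma-Poisson, with 17 or 33 GPs per arm. The ratio 1.57 is 14.9/9.5, from the coverage changes in section 2.4, used only as an illustration.

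| Setting | Non-overlapping | Cumulative |
|---|---|---|
| No arm effect, GP rates stable (means 2–10, variance 0–1) | 0.038–0.066 | 0.010–0.021 |
| Constant ratio 1.57 (mean 5, variance 0.5) | 0.055–0.056 | 0.015–0.017 |
| Constant ratio 2 (mean 5, variance 0.5) | 0.045–0.048 | 0.011–0.013 |
| No arm effect, GP-by-period log-SD 0.3 / 0.6 / 1.0 (33 per arm, mean 5, variance 0.5) | 0.098 / 0.275 / 0.498 | 0.033 / 0.157 / 0.373 |

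A constant arm effect leaves the rejection rate where it is under no effect. Overlap makes the test conservative; appreciable variation of GP rates between periods turns this into inflation.

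**4. Pearson on pooled doses.** This tests the T0–T6 doses of the two arms against equal shares. With mean μ doses per GP and between-GP variance k, the variance inflation is V = 1 + kμ, and the rejection rate under the null is 2·(1 − Φ(1.96/√V)):

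- μ = 2, k = 0.25: V = 1.5, rate 0.110
- μ = 5, k = 0.5: V = 3.5, rate 0.295
- μ = 5, k = 1: V = 6, rate 0.424
- μ = 10, k = 1: V = 11, rate 0.555

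Simulation under unstratified allocation agrees:

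| Mean doses per GP | k = 0 | k = 0.25 | k = 0.5 | k = 1 |
|---|---|---|---|---|
| 2 | 0.05 | 0.10–0.12 | 0.16 | 0.23–0.24 |
| 5 | 0.04–0.05 | 0.18–0.20 | 0.30 | 0.42 |
| 10 | 0.05 | 0.30 | 0.42–0.44 | 0.54–0.57 |

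**5. Effect of stratification.** Section 2.2 stratifies on estimated baseline HPVv count, which removes part of the between-GP variation. With balanced allocation on the four categories (34 or 66 GPs in all, an accurate three-month baseline count, no practice clustering) and k from 0.5 to 1, rejection is 0.14–0.21 at mean 2, 0.22–0.30 at mean 5 and 0.26–0.35 at mean 10.

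**6. Pearson on GPs by count category.** With GPs grouped as 0, 1–5, 6–10 and 11 or more doses, null rejection is about 0.03–0.06. Practice clustering was not simulated.

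**The case against.** The strongest reply concerns Pearson and Fisher. A reader might infer that the SAP treats doses as independent binary observations, but section 4.2.1 does not say so. Section 4.2.3 defines the outcome per GP and section 3.3.1 already groups baseline counts into four categories, so a table of arm by GP count category is a fair reading. It is close to nominal apart from practice clustering. This stands: the defensible charge is that the unit and table are undefined, so that both a nearly valid and a badly invalid test fit the wording.

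A reader might also infer that overlapping time points inflate all these tests. They do not. The Pearson/Fisher sentence covers a single window, T0 to T6, and overlap by itself makes the trend test conservative. Section 7 speaks of the primary and secondary outcomes, so applying its cumulative definition to section 4.2.1 is itself an inference. The trend test nevertheless misses a constant arm effect on non-overlapping counts too.

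The high pooled-dose figures depend on assumed means of 5 to 10. GPs who gave no HPVv in the previous six months are eligible (section 2.1.1), so lower means are plausible.

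Finally, the tests are labelled descriptive, and secondary outcomes are exploratory under section 3.1. That limits the consequence, but it does not make a test answer the question the SAP assigns to it.

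**Conclusion.** The Cochran-Armitage test is wrong as specified. Under neither reading of the counts does it compare the arms, and on cumulative columns it is also miscalibrated. This part needs no assumption about the size of between-GP variation.

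The Pearson and Fisher tests are underspecified. How far they err depends on the table chosen and on the assumed means and variances, from near nominal by GP category to badly inflated on pooled doses. The figures in the working are conditional on those assumptions and are not estimates for this trial.

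It would be tempting to conclude that the trial's main result is at risk. The documents do not support that: sections 3.1 and 4.2.3 rest the primary decision on the arm coefficient of the mixed model, and secondary objectives 1 and 2 use analogous models. For objectives 6 and 7, section 4.1.2 speaks only of description while section 4.2.4 adds group tests that ignore clustering; the size of that error was not quantified. The change should be made, but the primary analysis does not depend on it.

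**What to change.** - In section 4.2.1, delete the Cochran-Armitage, Pearson and Fisher tests of HPVv counts. Describe counts per GP by arm, stating whether first doses or all doses are meant.
- Take arm comparisons of counts from the mixed models in sections 4.2.3 and 4.2.4. Their main versions have GP intercepts only, so read them beside the practice-level sensitivity analysis of section 4.2.5.
- If a time trend is wanted, model the non-overlapping intervals T0–T3, T3–T6 and T6–T12 with a log(length) offset and an arm-by-interval term.
- For objectives 6 and 7, report descriptively, or use a model that accounts for GP and practice clustering.

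If the sponsor wishes to keep a simple test of counts, the minimum is to name the GP as the unit, define the categories, and state that practice clustering is ignored.

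The cost is SAP wording, slightly more modelling if a trend is wanted, and fewer simple p-values in the report. No new data are needed; section 3.3.2 already has doses documented from T0 to T12.
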